1.0 Introduction

Growing concerns have been raised with respect to vaping among youth, with substantial increases observed in recent years within Canada and the United States (Cole, Aleyan, Battista, & Leatherdale, 2020; Hammond et al., 2019). Within England, vaping experimentation has increased, whereas regular use has remained fairly stable over time (McNeill et al., 2019). It remains unclear what may be driving these cross-country differences; however, it may be due to differences in e-cigarette regulatory frameworks. For instance, within the United Kingdom, there are limits set on the nicotine concentration present within e-cigarettes (20 mg) and marketing of e-cigarettes is restricted to local channels (e.g., billboards, posters) (UK Government, 2016). In contrast, within Canada, e-cigarette marketing is permitted through mass media channels, such as radio, television and print providing the content of advertisements do not appeal to youth or include lifestyle advertising (Health Canada, 2018). Furthermore, the maximum nicotine content permitted in e-cigarettes is 66 mg/ml (Health Canada, 2018). In the United States (US), there are few federal restrictions on e-cigarette marketing and there are no limits on the amount of nicotine permitted in e-cigarettes (Sharpless, 2019).

Concerns about youth exposure to nicotine from vaping have also increased in light of the advent of nicotine salt technology that enables the delivery of higher concentrations of nicotine. In contrast to free-base nicotine, nicotine salt products facilitate the delivery of higher concentrations of nicotine while reducing the nicotine impact on the upper airways (Talih et al., 2019) and are designed to improve the sensory experience of e-cigarette use. This may be important for new e-cigarette users and may have played a role in the popularity of ecigarette use among young people, including those who have never smoked. Other health concerns include the outbreak of acute lung diseases (E-cigarette, or Vaping product use Associated Lung Injury (EVALI)) that occurred in 2019, mostly in the US. The US Centers for Disease Control and Prevention (CDC) have attributed vitamin E acetate-contaminated tetrahydrocannabinol (THC)-vaping products (vitamin E acetate is used to thicken THC oils) as the culprit in the EVALI outbreak (Centers for Disease Control and Prevention (CDC), 2020) rather than nicotine vaping products. Given the popularity of e-cigarettes as a drug delivery system, it is possible that some youth in England may be using e-cigarettes to vape illegal THC and other products. However, there have been no surveys conducted to date in England investigating the possible health effects of e-cigarette use among youth.

Concerns about the potential health effects of vaping among youth in the US have increased the urgency for research in this area. To that end, biomarker studies provide an opportunity to generate timely evidence enabling the examination of potential health risks of e-cigarette use among youth. Additionally, international studies that facilitate comparisons across countries with divergent e-cigarette regulatory environments may provide a deeper understanding of what may be driving differences in rates of e-cigarette use in England versus Canada/the US.

2.0 Study Aims

The current study extends an existing **international survey (the ITC Youth Tobacco and Vaping Surveys) and associated Biomarker Sub-Study** led by [name] from the University of Waterloo to answer important questions about the impact of English vaping policies on vaping and its health consequences among a sample of youth.

Aims for NIHR study: To compare vaping and smoking patterns and toxicant and nicotine exposure, and respiratory symptoms among youth (16-19 years old) who vape with youth who smoke, vape and smoke, and youth who do neither, in England, compared with youth in Canada and the US that have different e-cigarette regulations.

Research Questions for NIHR study:

- 1. How do patterns of vaping and smoking among youth in England compare with patterns in Canada and the US, which have different e-cigarette regulations?
- 2. How does exposure to potential toxicants and nicotine differ between *youth vapers, smokers, dual users and non-users*, in England compared with Canada and the US?
- 3. How does exposure to potential toxicants and nicotine differ between *youth vapers of nicotine salt products* in England compared with Canada and the US?
- 4. What is the association between e-cigarette use and reported respiratory symptoms among youth in the three countries?

We will conduct patient and public involvement with young people to inform research and dissemination.

2.1 Outcomes/Endpoints

ITC Youth Tobacco and Vaping surveys

Primary: smoking and vaping status, including frequency of smoking and vaping between England and US/Canada.

Secondary:

- respiratory symptoms reported by past-week vapers, smokers, dual users and nonusers
- e-cigarette type/product(s), brand(s) and flavours used
- use of vaping products with nicotine (including nicotine content and nicotine salts)
- measures of nicotine dependence
- differences in susceptibility measures for smoking and vaping among non-users between England and Canada/US

Biomarker sub-study

Primary: a comparison of the four different types of biomarker data (nicotine metabolites, the tobacco-specific nitrosamine 4-(methylnitrosamino)-1-(3-pyridyl)-1-butanol (NNAL), volatile organic compounds (VOCs), Polycyclic aromatic hydrocarbons (PAHs), across past-week vapers, past-week dual users, past-week smokers and non-users (of tobacco, vaping products, or cannabis in the past 30 days) between England and Canada/US.

Secondary: biomarker differences between nicotine salt e-cigarette users in England compared to Canada/US.

3.0 Study Methodology

3.1 ITC Youth Tobacco and Vaping Survey

The ITC Youth Tobacco and Vaping Survey is an online survey that was designed to examine the uptake of nicotine vaping products (NVPs) among youth in three countries with different policy environments: the United States (US), Canada and England (Hammond et al., 2019; Hammond, Reid, & Boudreau, 2020; Hammond, Reid, Rynard, & Burkhalter, 2020; Hammond, Reid, White, & Boudeau, 2018). The ITC Youth Tobacco and Vaping Survey included questions on the use of e-cigarettes (all models) and tobacco use (including manufactured and rolling tobacco). Questions also included self-reported dependence to various products (e.g. by asking participants 'do you consider yourself addicted to cigarettes/e-cigarettes', urges to use the product and measuring self-reported frequency of smoking, vaping and dual use).

The ITC Youth Tobacco and Vaping Surveys were initially administered annually during the first three waves of the study (W₁: 2017, W₂: 2018, W₃: 2019), and were originally funded by US NIH. However, in light of recent increases in youth e-cigarette use observed in Canada (Cole, Aleyan, Battista, & Leatherdale, 2020; Hammond et al., 2019), the ITC Youth Tobacco and Vaping Surveys were enhanced with funding from Health Canada to include additional half-yearly surveys (2020a, 2021a, with the original surveys becoming 2020b and 2021b) and four-week follow-up surveys. The additional half-yearly surveys and four-week follow-up surveys were added to enable more rapid and detailed assessment of vaping patterns among youth in Canada, the US and England. The four-week follow-up survey was also designed to examine patterns of smoking and vaping use and dependence in more depth, including transitions to more frequent vaping use and the potential emergence of nicotine dependence among youth. Technical reports are available at http://[name].ca/projects/e-cigarettes/itc-youth-tobacco-ecig/

3.1.1 Eligibility Criteria

Inclusion Criteria

Eligible respondents for ITC Youth Tobacco and Vaping Surveys include youth aged 16-19 from Canada, England and the US at the time of recruitment. Initially the recruitment criteria only included youth aged 16-19 but were to be extended to include 20-29 year olds for the 2020b wave only.

Exclusion Criteria

No exclusion criteria exist, except age (as described above) and not residing in England, Canada, or the US (residents of the territories were excluded in Canada).

3.1.2 Recruitment Procedures

The sample is recruited from the Nielsen Consumer Insights Global Panel, which maintains panels in the Canada, England and the US. The Nielsen panel is recruited using both probability and non-probability sampling methods in each country (Czoli, Goniewicz, Palumbo, White, & Hammond, 2018).

Respondents are recruited either directly or through their parents. Email invitations are sent to a sample of panellists that met the eligibility criteria. Panellists who were known to be parents were also contacted. Parents who confirm they had one or more children aged 16-19 living in their household were also contacted.

3.1.3 Consent Procedures

After screening participants for eligibility, all potential respondents are provided with information about the study; specifically, an onscreen information letter is provided in the online survey. This page is shown to all potential respondents when they first log into the survey. The survey explicitly asks respondents to indicate whether they consented to participate in the study.

Participants have the option to withdraw their participation in the study at any time by not submitting their responses to the survey questions (i.e., not clicking 'next' to advance to the next question or to the end screen, or closing the browser window before completing the survey).

3.1.4 Participant Remuneration

Respondents receive remuneration in accordance with their panel's usual incentive structure, which could either include monetary awards or points-based rewards and/or chances to win monthly prizes.

3.1.5 Study Setting

These are completed online by participants in Canada, England and the US.

3.2 Biomarker Sub-Study

The funding obtained from Health Canada (described in Section 3.1) has been used to establish the biomarker sub-study. Briefly, this sub-study involves participants completing a short questionnaire and providing a urine sample. The biomarker sub-study aims to examine biomarkers of exposure to vaping products and cigarette smoking among young people, including associations with frequency of use and types of vaping product(s) used.

3.2.1 Eligibility Criteria

Inclusion Criteria

Eligible respondents include youth aged 16-19 from Canada, England and the US at the time of recruitment who were current participants of the ITC Youth Tobacco and Vaping survey described above (Refer to Section 3.1) and who belonged to a panel that allowed researchers to approach respondents for inclusion. They also need to pass the data quality question in the ITC Youth Tobacco and Vaping survey (i.e., asking respondents what the current month was), have parental permission to participate if under 18, and be living at an address where they would be able to receive mail for at least the next four weeks and provide their contact information including postal address. They had to be in one of four groups:

- 1) Past week vapers only
- 2) Past week smokers only
- 3) Dual users (past week smokers and vapers)
- 4) Non-users (no tobacco or vaping product or cannabis use in the last 30 days)

Exclusion Criteria

No exclusion criteria exist, except age and participation in the ITC Youth Tobacco and Vaping survey, as described above and their responses placing them in one of the four eligible groups.

3.2.2 Recruitment Procedures

The sample for the biomarker sub-study is recruited from our existing sample of youth participating in the ITC Youth Tobacco and Vaping survey. At the end of the survey, respondents that are part of a panel that allowed participant contact and are also eligible and interested in participating in the biomarker sub-study are told that they may be selected for this additional study. Among those who are selected to participate in the biomarker sub-study, an email is sent to confirm they are still interested in participating in the study before a kit is sent.

3.2.3 Consent Procedures

At the end of the ITC Youth Tobacco and Vaping survey, participants are provided with information about the biomarker sub-study and what is involved in participation. Participants are then asked to provide their consent to participate in the biomarker sub-study. Those who are under the age of 18 are asked to have their parent/legal guardian consent to their participation in the biomarker sub-study. Those who consent to participating in the biomarker sub-study are sent a short questionnaire, a urine collection kit, instructions and shipping materials.

3.2.4 Data Collection

Short Questionnaire

Participants in the biomarker sub-study are asked to complete a short pen and paper questionnaire designed to collect data on past-week e-cigarette use, tobacco use and cannabis use, at the time of their bio-sample collection. Measures are also included to examine last e-cigarette used, including flavours used, nicotine concentrations, brand and nicotine salt or non-salt e-liquid.

Bio-Sample Collection

Participants are advised to collect their urine sample as soon as possible (ideally within the next 5 days). Participants are provided with 'what to do' instruction sheets to guide them on how to collect their urine sample, pack the sample and post the sample and short questionnaire. Shipping materials are pre-labelled with unique numeric ID labels to ensure unique participants can be identified while preserving anonymity during transit and storage.

3.2.5 Bio-Sample Procedures

Bio-Sample Shipping & Storage

After study participants from England have collected a urine sample, the kit and questionnaire are sent to King's College London using postage paid envelopes, in order to ensure no personal information is linked to participants and that the anonymity of participants is maintained. Once the samples are received by King's College London's research facilities, the genetic material is removed from the urine samples by centrifuge within seven days of receipt. The samples are then stored in a -20 degree Celsius freezer until all the samples have been collected. Once the collection of all samples is complete, the samples are sent to the Roswell Park Comprehensive Cancer Centre in Buffalo, New York, US.

For participants in the US the kit and questionnaire are sent directly to Roswell Park Comprehensive Cancer Centre in Buffalo. For participants in Canada, the kit and questionnaire are sent to the University of Waterloo for processing before being sent to Roswell Park Comprehensive Cancer Centre in Buffalo once collection was complete.

Sample Analysis

At Roswell Park Comprehensive Cancer Centre, the samples will be analysed to provide estimates of exposure to potentially harmful constituents across the four user groups (past week vapers, past week smokers, past week dual users, and non-users) in all three countries. Urine samples will be tested using highly selective mass spectrometric methods (Goniewicz et al., 2018; Shahab et al., 2017) for: a) nicotine metabolites (including cotinine and hydro cotinine); (b) NNAL which is a metabolite of the tobacco-specific nitrosamine NNK; (c) Volatile Organic Compounds which test exposure to numerous toxic chemicals present in smoke, and in small quantities in vaporised products (including acrolein, acrylonitrile, acrylamide, and benzene metabolites); (d) Polycyclic aromatic hydrocarbons (PAHs), which are a toxic by-product of combustion and enable identification of any combustion occurring in the products; and (e) Creatinine, for correction.

All sample testing will be undertaken at Roswell Park Comprehensive Cancer Centre, to ensure comparability across countries. Analysing samples at different laboratories is likely to introduce laboratory specific batch effects due to the use of different sample preparation, instruments, and/or data analysis pipelines (Gika et al., 2010).

3.2.6 Participant Remuneration

Participants of the biomarker sub-study are provided with an Amazon gift card.

3.2.7 Study Setting

Urine kits are sent out to participants to complete at home, along with the short questionnaires that are to be completed by participants using paper and pencil. Participants in England then post their samples to King's College London to remove genetic material and for temporary storage, before they are sent in batches to the US Roswell Park Comprehensive Cancer Centre for biomarker analysis following a tested protocol (Shahab et al., 2017).

3.3 NIHR-funded Enhancements

NIHR funding is being used to enhance the above studies in several ways, including to build overall capacity in England to analyse the ITC youth survey data. An overview of the main enhancements made under the NIHR study are described in further detail below (see also yellow shading in Figure 1).

Figure 1: Study Flow Chart (Yellow shading denotes NIHR enhancements)

3.3.1 ITC Youth Tobacco and Vaping Survey enhancement

Additional questions on the presence of respiratory symptoms are added to the ITC Youth Tobacco and Vaping survey (Survey Wave 2020b onwards). Questions were adapted from the WHO Health Behaviour of School-aged children survey on asthma and wheezing (Hublet, De Bacquer, Vereecken, & Maes, 2004; Lochte, Petersen, Nielsen, Andersen, & Platts-Mills, 2018). Questions also replicated those used in a randomised controlled trial of e-cigarettes for smoking cessation (Hajek et al., 2019). These questions examine whether respondents had experienced various respiratory symptoms including shortness of breath, wheezing, chest pain, a cough and the presence of phlegm.

3.3.2 Biomarker Sub-Study enhancement

We sought to enhance the sample size of the biomarker sub-study to allow for the examination of cross-country comparisons (i.e., between England versus the United States/Canada). An overview of the recruitment targets set out for the biomarker sub-study are given in Figure 1. In summary, an additional 240 participants would be recruited to give bio-samples.

4.0 Statistical Analysis for NIHR-funded study

4.1 Biomarker Analysis

Using T-tests and one-way ANOVAs, we will compare biomarkers of exposure to: a) nicotine metabolites (including cotinine and hydroxycotinine); b) NNAL; c) VOCs and metabolites; d) PAHs and; e) creatinine among **past-weekly vapers** in England versus those in Canada and the US. These comparisons will also be tested on each outcome of interest described above using multivariable linear regression, adjusting for relevant sociodemographic and behavioural covariates. These covariates include indicators of socio-economic status (SES), family/friends' smoking behaviours, grilled meat consumption, smoking cannabis, smoking tobacco, vaping cannabis, other tobacco use and the use of nicotine replacement therapy (NRT).

Similar analyses will be conducted to compare *biomarkers of exposure* among (i) **past-weekly dual users;** (ii) **past-weekly smokers;** ;(iii) **non-users**; and (iv) **nicotine salt vapers,** in England versus Canada/US.

4.2 Support for Analysis of ITC Youth Tobacco and Vaping Survey Data

Using multivariable logistic regression, we will examine differences in *frequency of smoking and vaping* among youth in England versus those in Canada/US. Logistic regression models will adjust for relevant covariates including age, sex, race/ethnicity, indicators of SES and tobacco/cannabis use.

Using multivariable logistic regression, we will compare how the *type of e-cigarette product used, use with nicotine, nicotine content, e-cigarette brand, use of nicotine salts and measures of nicotine dependence* differ among vapers in England versus vapers in Canada/US. Logistic regression models will adjust for relevant covariates including age, sex, race/ethnicity and indicators of SES.

Using multivariable logistic regression, we will compare differences in *measures of susceptibility* among non-vapers/non-smokers in England compared to non-vapers/non-smokers in Canada/US. Logistic regression models will adjust for relevant covariates including age, sex, race/ethnicity, SES indicators, tobacco/cannabis use, alcohol use, and family/friends' use.

4.2.1 Analysis of Respiratory Symptoms Data *Primary Comparison*

Using bivariate logistic regression, we will compare *the prevalence of respiratory symptoms including a*) *shortness of breath; b*) *wheezing; c*) *cough and; d*) *phlegm* among **past-weekly vapers** in England versus those in Canada/US. Group comparisons will also be conducted on each outcome of interest described above using multivariable logistic regression models adjusting for relevant covariates. Analyses will include self-reported COVID-19 symptoms, symptoms of asthma and information on past smoking and vaping behaviour.

Similarly, bivariate and multivariable logistic regression will be used to compare the *prevalence of respiratory symptoms* among (i) **past-weekly dual users**; (ii) **past-weekly smokers**; and (iii) **non-users** in England versus Canada/US.

Secondary Comparison

Using bivariate logistic regression, we will compare *the prevalence of respiratory symptoms including a*) *shortness of breath; b*) *wheezing; c*) *cough and; d*) *phlegm* among exclusive vapers versus exclusive smokers. These comparisons will also be tested on each outcome of interest using multivariable logistic regression models, adjusting for relevant covariates. Analyses will include self-reported COVID-19 symptoms, symptoms of asthma and information on past smoking and vaping behaviour.

Similarly, bivariate and multivariable logistic regression models will be used to compare the prevalence of respiratory symptoms among (i) vapers versus dual users (i.e., smokers and vapers); (ii) vapers versus non-smokers/non-vapers; and (iv) nicotine salt vapers in England versus Canada/US.

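### Respiratory symptoms: no stated analysis estimates the vaper versus non-user association by country, or tests whether it differs between England and Canada/US

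*Protocol*

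**What the plan says.** Section 2.0 of the protocol presents the study as one "to answer important questions about the impact of English vaping policies on vaping and its health consequences among a sample of youth". Its aim is to compare use patterns, exposure and respiratory symptoms among youth "who vape with youth who smoke, vape and smoke, and youth who do neither, in England, compared with youth in Canada and the US". Research question 4, the only one on symptoms, asks: "What is the association between e-cigarette use and reported respiratory symptoms among youth in the three countries".

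Section 4.2.1 sets out the analysis.

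- **Primary Comparison.** Symptom prevalence is compared among past-week vapers "in England versus those in Canada/US. Group comparisons will also be conducted on each outcome of interest described above". The first step is bivariate logistic regression; the second is "using multivariable logistic regression models adjusting for relevant covariates". On covariates it says: "Analyses will include self-reported COVID-19 symptoms, symptoms of asthma and information on past smoking and vaping behaviour". The same country contrast is then run within dual users, within smokers and within "iii) non-users in England versus Canada/US".
- **Secondary Comparison.** User groups are compared with each other, including "ii) vapers versus non-smokers/non-vapers". These contrasts are not stated to be by country.

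No country by user-group term is named in either part. Section 2.1 lists respiratory symptoms as a secondary survey outcome.

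**The concern.** Everyone in the leading primary model vapes, so that model cannot estimate an association between vaping and symptoms. Its country odds ratio combines any difference in the effect of vaping with whatever else differs between the countries. The planned covariates deal with part of this (COVID-19 symptoms, asthma symptoms, past use). Climate, air quality and the way young people answer symptom questions are not covered.

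The non-user model would show a background difference, but as a separate result. Setting one stratum's result beside another's is not a test of whether they differ, particularly when the vaper stratum is much smaller than the non-user stratum.

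What is at stake is interpretation. Section 2.0 links the study to the health consequences of English policy, and section 12.2 plans briefings for policy-makers. Without the contrast of contrasts, the report would contain no estimate on which to say that the vaping-symptom association is stronger, weaker or the same in England. A background difference could look like a difference in that association, or an opposite one could hide it.

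**Working it through.** **The plan's own figure.** The only survey power statement (section 4.3.1) concerns frequent vaping: 4,000 per country, base rate 1.9%, two-sided alpha 0.05, power 0.80, detectable difference about 1.0 percentage point. It reproduces: the detectable difference is 0.95 points upward, and power for 1.9% versus 2.9% is 83%. It does not bear on symptoms. The protocol gives no symptom rates and no number of vapers, so every input below is an assumption except the two-sided 5% level.

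**Structure.** Let θ be the odds ratio for vaping, equal in both regions. The odds of a symptom in vapers are θ times the odds in non-users of the same region. The country odds ratio among vapers is then

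(θ × odds, Canada/US non-users) / (θ × odds, England non-users) = background country odds ratio.

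θ cancels, whatever rates are assumed.

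**Illustration.** Assume non-user prevalence of 15% in England and 20% in Canada/US, and θ = 1.5.

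- England vapers: odds 0.1765 × 1.5 = 0.2647, prevalence 20.9%.
- Canada/US vapers: odds 0.25 × 1.5 = 0.375, prevalence 27.3%.
- Country odds ratio in vapers, Canada/US to England: 0.375 / 0.2647 = 1.42 (0.71 the other way round), log 0.348.

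Assume 320 vapers in England and 640 in Canada/US, with the variance of each log odds equal to 1/[n p(1−p)].

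- SE = √(1/52.96 + 1/126.9) = √(0.01888 + 0.00788) = 0.164.
- z = 0.348 / 0.164 = 2.13, so the contrast is significant in about 57% of studies (33% with 160 English vapers, 74% with 480). With backgrounds of 18% and 20% and 320 English vapers it is about 13%.

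Add an assumed 3,000 and 6,000 non-users.

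- Ratio of odds ratios: SE = √(0.02676 + 1/382.5 + 1/960) = √0.03042 = 0.174, about 7% larger. Its true value here is 1.
- Non-user contrast alone: SE = √(0.00261 + 0.00104) = 0.060, z about 5.8. Vapers and non-users share exactly the same country odds ratio, yet one is almost always significant and the other about 57% of the time. This is why separate strata cannot be compared by their significance.

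**Range.** Simulation with 20,000 replicates per scenario, θ = 1.5, twice as many Canada/US as English vapers, and 2,800 English and 5,600 Canada/US non-users. Entries are the share of studies in which the vaper-only country contrast is significant.

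| Non-user prevalence, England v Canada/US | 200 English vapers | 400 | 600 |
|---|---|---|---|
| 10% v 10% | 5% | 5% | 5% |
| 10% v 13% | 21% | 41% | 57% |
| 10% v 15% | 49% | 80% | 93% |
| 15% v 20% | 38% | 67% | 84% |

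The test of the ratio of odds ratios rejects in 4.8-5.2% of studies throughout. Its SE is about 5% larger than that of the vaper-only contrast with 200 English vapers, 9% with 400 and 13-14% with 600. All these calculations are unadjusted; the planned covariates would shrink the background difference by an unknown amount.

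**The case against.** The strongest reply is that section 4.2.1 promises a comparison of prevalence and delivers one. It does not call the country odds ratio an effect of vaping or of regulation. The same section measures the background by comparing non-users across countries, and it plans adjustment for COVID-19 symptoms, asthma symptoms and past use. Research question 4 can be read as asking for the association overall, which the secondary vaper versus non-user contrast addresses, and the symptom paper in section 12.1 is described by user group with no country contrast. Respiratory symptoms are a secondary outcome, and an interaction term could be specified in an SAP not seen here.

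Much of this stands, and it rules out three stronger readings that a reader might infer.

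- *That the primary comparison is invalid or ignores the background rate.* It is a sound description of prevalence, and the non-user contrast is planned beside it.
- *That the percentages above are false-positive rates.* In those scenarios prevalence in vapers truly differs (20.9% v 27.3%), so they are the power of the stated prevalence test. They would mislead only if the result were read as a difference in the association with vaping.
- *That the protocol commits itself to reading the vaper-only result as a policy effect.* Section 2.0 gives the policy purpose, but section 4.2.1 makes no such claim.

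What the reply does not remove is the gap. The aim sets user groups against each other in England relative to Canada and the US, and question 4 refers to the three countries. Neither part of section 4.2.1 states the vaper versus non-user association by country or its comparison. The protocol itself fixes which contrasts are primary and secondary, so this is more than a detail left for later.

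**Conclusion.** The point holds as a gap between the question and the stated analyses. The within-group country contrasts describe prevalence correctly, but they cannot show whether the vaping-symptom association differs between England and Canada/US, and no other stated analysis does so.

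The structural result, that a common vaping odds ratio leaves only the background in the vaper-only contrast, needs no assumed rates. After adjustment it applies to whatever background difference the covariates leave. The size is illustrative only: an apparent odds ratio of 1.42 under assumed non-user rates of 15% and 20%, and none if the backgrounds are equal. The protocol's figures cannot say which is nearer the truth. For a secondary outcome this is an inexpensive improvement worth making, not a fault that undermines the study.

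**What to change.** Keep the planned within-group country contrasts as prevalence comparisons. Add to section 4.2.1 one logistic model per symptom containing country, user group (vaper, smoker, dual user, non-user), country by user group, and the planned covariates. From it, report the vaper versus non-user odds ratio by country and the ratio of these odds ratios, England to Canada/US, with a 95% CI. State that any claim that the vaping-symptom association differs by country will rest on that ratio and not on the vaper-only contrast.

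Two cautions belong in the text. Past smoking and vaping history is strongly tied to user group, so its place in this model needs thought; showing the ratio with and without it would be sensible. The ratio also does not isolate regulation, because who vapes may differ by country, and equal odds ratios on unequal baselines still imply unequal risk differences.

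The cost is wording, a little more analysis and a somewhat wider interval: about 5-14% on the standard error, unadjusted and under the assumed sample sizes. The survey already covers all four groups, so no new data are needed.
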